5.4 Serious Adverse Event (AE) Reporting

5.4.1 In accordance with our study specific safety monitoring plan as well as the SHC-Cincinnati Safety Monitoring Process for Clinical Research CR 6.10 SOP, patients will be closely scrutinized by clinical investigators for AEs. Even though there are no known serious side effects reported with HT therapy, subjects will be screened for dizziness, headache, and restlessness prior to the intervention/control session. In addition, subjects will be evaluated during the HT, sham and control/presence groups for emotional outburst, muscle spasm and restlessness during the study intervention time as well as any changes in the status of dizziness or headache following the study intervention period. Continued monitoring will occur until end of study (up to 8 hours postoperatively) to assess for persistent treatment effect.

5.4.2 Any Serious **and** Unexpected AE and Grade 3 or above, with a reported causality of “possible,” “probably,” or “likely” must be reported to the Study PI and Medical Staff Co-Investigator in an expedited method.

5.4.3 All reported AEs will be classified using the Common Terminology Criteria for Adverse Events (CTCAE), version 4.

5.4.4 Each AE is associated with a grade. Grade refers to the severity of the AE. The CTCAE v4.0 displays Grades 1 through 5 with unique clinical descriptions of severity based on this general guideline: Grade 1 = mild, Grade 2 = moderate, Grade 3 = Severe, Grade 4 = Life-threatening or disabling, Grade 5 = Death.

5.4.5 Grade 4 or 5 events must be reported to Study PI within 24 hours with written documentation of the event filed within 7 days of the event.

5.4.6 CCHMC’s IRB must be notified of any Serious **and** Unexpected adverse event within 7 days.

5.4.7 Study PI will ensure that SHC home office and all applicable regulatory organizations are notified per regulatory guidelines.

5.4.8 Study PI will notify all participating investigators of any reported SAE associated with the trial.

5.5 Annual Reporting

The principal investigator will report all other safety events to the CCHMC IRB consistent with current institutional policy/SOP. Serious AEs that do not meet the criteria for expedited reporting as well as non-serious adverse events will be reported at the time of submission of annual IRB Progress Reports. Likewise, minor deviations will be reported in annual reporting to the CCHMC IRB. All other reportable events will be conveyed to the CCHMC IRB office, in summation form, at the completion of the study.

6.0 Data Handling and Record Keeping

6.1 The specific variables involved in data collection are detailed under study procedures and reflected in CRFs as well as within the listing of Sleep 7 source documents.

6.2 Data collection for this study will primarily be through an online data management system housed on SHC servers. Members of the SHC research team will enter data into SHC system with unique user IDs and passwords. All secure web-based information transmission is encrypted and complies with HIPAA security guidelines and 21 CFR 11.

6.3 Confidentiality and Security

- 6.3.1 Information about study subjects will be kept confidential and managed according to the requirements of HIPAA.
- 6.3.2 Access to data collected for this study is limited to study investigators.
- 6.3.3 In the event that a subject revokes authorization to collect or use PHI, the investigator, by regulation, retains the ability to use all information collected prior to the revocation of subject authorization. For subjects that have revoked authorization to collect or use Private Health Information (PHI), attempts should be made to obtain permission to collect at least vital statistics (i.e. that the subject is alive) at the end of their scheduled study period.
- 6.4 Source Documentation
 - 6.4.1 Source data are contained in source documents. Examples of original documents and data records specific to this study include: hospital records and PSG reports.
 - 6.4.2 When observations are entered directly into a computerized system, the electronic medical record (EMR) or other electronic record (ex. PSG) is the source document. Examples of EMR source documentation specific to this study include: patient demographics, medication records, time in PACU, vital signs, pain scores, and laboratory parameters.
 - 6.4.3 Select data will be recorded directly on case report forms. These forms will be used as “source documentation” and include the intervention safety assessment, HT practitioner stress survey, the preoperative data collection form and HT satisfaction survey.
 - 6.4.3.1 All data requested on the CRF must be recorded.
 - 6.4.3.2 All missing data must be explained.
 - 6.4.3.3 If a space on the CRF is left blank because the procedure was not done or the question was not asked, write “N/D”.
 - 6.4.3.4 If the item is not applicable to the individual case, write “N/A”. All entries should be printed legibly in black or blue ink.
 - 6.4.3.5 If any entry error has been made, to correct such an error, draw a single straight line through the incorrect entry and enter the correct data above it. All such changes must be initialed and dated. DO NOT ERASE OR WHITE OUT ERRORS. For clarification of illegible or uncertain entries, print the clarification above the item, then initial and date it.
- 6.5 Record Retention
 - 6.5.1 Clinical research records will be retained per SHC standard operating procedure on *Clinical Research Records Retention (MR-002)*.
- 6.6 Laboratory Specimens
 - Lab tests (CRP, glucose, cortisol and vitamin D25) will be processed and managed by SHC Laboratory Medicine.

7.0 Quality Control and Quality Assurance

- 7.1 Internal auditing will be performed quarterly to ensure that the data are accurate, consistent, complete and reliable and in accordance with ICH GCP guidelines and 21 CFR 11.
- 7.2 The study PI will assess the audit worksheet, classify type of discrepancy and develop appropriate action plan.

8.0 Statistical Considerations

- 8.1 All data will be managed and analyzed using SAS® Version 9.3 (SAS Institute, Cary, NC) unless otherwise stated for specialized analysis. Demographic and summary data will be compiled and entered into the SAS research database by a

trained data manager. The database has been in use for 14 years; it will be adapted for data entry specific to the new project. The database is stored on SHC's dedicated network drive. The network is security- and backup- protected by SHC information systems on a daily basis. In addition, the individual study files are password protected. The programs are run by the statistician and verified by a research investigator. Prior to embarking on any analysis, variables will be checked for outlying values. Distributional properties of the continuous variables will be examined and any transformations necessary for analysis considered. Bivariate comparisons will follow, to look at differences in baseline variables between HT and control groups (ex. age, gender and race, also length of time and type of surgical procedure e.g. burn versus other reconstructive procedure). These latter variables are potential covariates for secondary analysis. Analysis of variance (ANOVA) or Kruskal-Wallis test and Chi-square analysis will be used for these comparisons. Similarly, the association between outcome variables and baseline variables will be examined; correlation and ANOVA or Kruskal-Wallis will be used as appropriate.

8.2 The first approach for a clinical trial is usually intent-to-treat analysis. In the case of a missing end-point, where possible, the subject will be assigned to the "worst" possible value. However, this is not feasible for our sleep outcomes. A second approach would be to include those subjects with outcome data, complete case analysis. Last observation carried forward is also commonly used, but this method can be biased, but will be examined. Multiple imputation (MI) methods have been proposed^{92,104,105} and may be superior, but are not without problems, mainly bias with respect to missing data. In case the missing mechanism is not missing completely at random,¹⁰⁶ we will conduct a missing data analysis to address the question of bias. If the missing mechanism depends on group assignment (HT, sham or one of the control groups) or other demographic variables, we will estimate the bias using logistic regression. Bias adjusted analyses would then be conducted using the inverse of the estimated probability of being missing as the weighting factor. We will be able to do this by applying a weighted generalized estimating equations (GEE) method.¹⁰⁷ Thus we will use MI or weighted GEE method as appropriate, as well as complete case analysis. In general, it will be appropriate to use generalized linear random effects mixed model for analysis. This will allow for repeated nature of the outcome variables, and specification of the appropriate link function, dependent upon the type of outcome variable. SAS PROC GENMOD may be used for these analyses and using PROC GLIMMIX would also allow invocation of the GEE method if required. As mentioned above, bivariate relationships between outcome variables and independent variables will be examined; this will also be in preparation for consideration of any secondary analyses incorporating covariates and confounders. Variables considered as potential covariates in an initial model will either be those considered clinically significant irrespective of the statistical association and those associated with the outcome and independent variable of interest at $p < 0.15$. Inclusion in final models will depend upon statistical significance ($p < 0.05$) or effect of removal of the variable on the beta coefficient ($> 10\%$ change) on the independent variable of interest. Age and gender will be considered clinically meaningful and will be retained in the model independent of statistical significance.¹⁰⁸

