The measures targeted are TST, sleep efficiency, REM sleep and WASO. This Table shows data from a pilot cross-over study (median and 25th and 75th percentile) for the sleep variables of interest for 15 study subjects. In order to see the HT group with longer TST than the other groups, we will need a sample size of 50 per group for 80% power to detect a difference of 35 minutes, standard deviation of 70, assuming a 2-sided test and type I error rate of 0.016 to account for multiple testing. Similarly for sleep efficiency, we hypothesize a difference of 2% whereas in a previous study we observed a difference of 10%.³¹ Using the sample size of 50 per group we would be able to detect a difference of 7% with a standard deviation of 15, 2-sided test and type I error rate of 0.016, to account for comparing HT to the 3 control groups. Because the percentages depend upon another time dependent variable, the power is based on REM minutes. Using REM minutes, 50 subjects per group would enable us to detect a 15 minutes difference in REM sleep, assuming a standard deviation of 30, power of 80% and a 2-sided test. For WASO, with an assumed standard deviation of 50, a type 1 error rate of 0.016, a power of 80% and a 2-sided test, a difference of 25 minutes will require 50 subjects in each group, producing a total sample size of 200 subjects.

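### The missing-data weight in Section 8.2 is inverted: observed subjects should be weighted by 1/P(observed), not 1/P(missing)

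*Combined protocol and SAP*

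**What the plan says.** Section 8.2 lists several approaches to missing outcomes. It rules out worst-value assignment for the sleep outcomes and says that last observation carried forward will be examined, while noting that it can be biased. The passage at issue comes next. The trigger is "If the missing mechanism depends on group assignment (HT, sham or one of the control groups) or other demographic variables", in which case "we will estimate the bias using logistic regression". The adjusted analyses are then to be run "using the inverse of the estimated probability of being missing as the weighting factor", by "applying a weighted generalized estimating equations (GEE) method". The paragraph concludes: "Thus we will use MI or weighted GEE method as appropriate, as well as complete case analysis".

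No other section defines the weight or states it as the inverse probability of being observed. The sentence is complete, so neither redaction nor text extraction explains it.

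Two other statements bear on the consequence. Section 8.2 keeps age and gender in the model whatever their significance. Section 8.3.1 repeats that they are kept, but places covariate adjustment in secondary analyses. The planned main comparison in Section 8.3.1 is a generalized linear random effects model, not the weighted GEE.

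**The concern.** Inverse-probability weighting lets each observed subject stand in for similar subjects whose outcome is missing. A subject from a group in which 70% are observed should count 1/0.70 = 1.43 times. The stated rule gives that subject 1/0.30 = 3.3 and gives a subject from a group with 5% missing 1/0.05 = 20. The ordering is reversed, and the weight grows without limit as P(missing) approaches zero.

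At stake is the analysis meant to remove bias from missing data. Polysomnography is done on one night only (Section 4.2), so the sleep endpoints have no earlier recording to carry forward, and Section 8.2 calls worst-value assignment infeasible for them. That leaves multiple imputation, the weighted GEE and complete cases. If the weighted GEE is chosen and coded as written, it can add bias, and checking the code against the plan would confirm the wrong weight.

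**Working it through.** No figure in the plan depends on this weight, so there is nothing to reproduce. The check is algebra plus assumed scenarios.

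**Inputs from the documents.** The weight rule (Section 8.2); the age strata 5 to 11 and over 11 years (Section 4.1.1); and, for scale, the planning difference in total sleep time (TST), "80% power to detect a difference of 35 minutes, standard deviation of 70" (Section 8.3.1). **Assumed:** all missing rates, stratum means and stratum-specific effects, and equal stratum sizes.

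**Formula.** With stratum share f, missing probability p, weight w and mean μ, the expected arm mean is Σ f(1−p)wμ / Σ f(1−p)w.

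- w = 1/(1−p) gives Σ fμ, the true arm mean.
- w = 1 (complete cases) weights strata by f(1−p).
- w = 1/p (as written) weights strata by f(1−p)/p.

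With two equal strata and p₁ < p₂, complete cases weight stratum 1 relative to stratum 2 by (1−p₁)/(1−p₂), already above 1. The stated rule multiplies that by p₂/p₁, also above 1. The arm mean therefore moves further in the same wrong direction.

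| P(missing) | 1/P(missing), as written | 1/P(observed) |
|---|---|---|
| 0.05 | 20 | 1.05 |
| 0.10 | 10 | 1.11 |
| 0.20 | 5 | 1.25 |
| 0.30 | 3.3 | 1.43 |

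**Scenario A, unadjusted, no true effect.** TST is 420 min in the younger and 370 in the older stratum in both arms (true mean 395). HT is missing 5%/20%, control 10%/10%.

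- HT as written: 0.95/0.05 = 19 and 0.80/0.20 = 4, so (19×420 + 4×370)/23 = 411.3.
- HT complete cases: (0.95×420 + 0.80×370)/1.75 = 397.1.
- HT with correct weights: 395.0.
- Control: 395.0 under all three, because missingness is the same in both strata.
- Spurious difference: 16.3 min as written, 2.1 for complete cases, 0 with correct weights. The first is 16.3/35 = 47% of the planning difference.

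*Same scenario with age stratum in an additive model:* cell means of 420 and 370 in both arms fit exactly with a zero group effect, so all three weightings return 0.

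*Same scenario with control missing 5%/15%:* 0.95/0.05 = 19 and 0.85/0.15 = 5.667, so control as written is (19×420 + 5.667×370)/24.667 = 408.5. The unadjusted difference is 411.3 − 408.5 = 2.8 min.

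**Scenario set B, unadjusted, true difference 35 min.** Control TST is 400/330 by stratum; HT is 435/365, except in the row where the effect varies.

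| Missingness (younger/older) | Complete cases | 1/P(observed) | 1/P(missing) |
|---|---|---|---|
| Group only: control 10%, HT 20% | 35.0 | 35.0 | 35.0 |
| 10%/30% in both arms, constant effect | 35.0 | 35.0 | 35.0 |
| 10%/30% in both arms, effects 15 and 55 min | 32.5 | 35.0 | 23.2 |
| HT 10%/30%, control 10%/10% | 39.4 | 35.0 | 55.6 |
| HT 5%/15%, control 5%/5% | 36.9 | 35.0 | 53.9 |
| Control 5%/15%, HT 10%/27% | 36.7 | 35.0 | 34.9 |

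- Row 2: the contrast is right, but both arm means are 20.6 min too high as written, against 4.4 for complete cases.
- Row 3: adjusting for stratum does not help. The weighted effect is (9×15 + 2.333×55)/11.333 = 23.2, where 9 = 0.9/0.1 and 2.333 = 0.7/0.3.
- Row 4: the HT mean as written is (9×435 + 2.333×365)/11.333 = 420.6, and 420.6 − 365.0 = 55.6. Adding stratum to an additive model returns 35.0 under all three weightings.
- Row 6: the arm-mean errors, about 19 min each, almost cancel.

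**Precision.** A simulation of row 4 with 50 per group and an assumed within-stratum SD of 60 gave standard deviations of the estimated difference of 13.1 (complete cases), 12.9 (correct weights) and 21.4 (as written).

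**The case against.** The strongest reply is that the consequence is narrow.

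- The weighted GEE is conditional. It is an alternative to multiple imputation, complete-case results accompany it, and no sample size or endpoint depends on it. This stands.
- A reader might infer that the stated weight always does worse than complete cases. For arm means in the two-stratum case it does. For the HT contrast it does not: bias is zero when missingness depends on group alone, which is the first trigger Section 8.2 names, and zero when all arms share the covariate pattern and the effect is constant. In row 6 the stated weight lands closer to the truth than complete cases (34.9 against 36.7), though only by cancellation.
- A reader might take 16 minutes as the expected bias. It comes from a selected, unadjusted scenario with a steep missingness gradient in one arm and none in the other. It falls to about 3 minutes when control is missing 5%/15%, and vanishes with age stratum in an additive model. The plan does retain age, but Section 8.3.1 puts covariates in secondary analyses and does not say that age enters by stratum, so an unadjusted weighted GEE remains possible. Adjustment also fails when the effect varies with age (row 3).
- The wording may be a slip that an experienced analyst would code correctly. That is plausible, but nothing in the documents says so, and correct coding would then depart from the written plan.

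**Conclusion.** The weight is wrong as written. Only subjects with observed outcomes contribute to the weighted GEE, so it needs 1/P(observed), and no other section corrects the rule. When missingness depends on a covariate related to outcome, the stated weight moves arm means away from the truth. It can bias the HT contrast when the missingness pattern differs by arm and the covariate is not in the model, or when the effect varies with the covariate.

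The size cannot be fixed, because the documents state no expected missing rate. Across the assumed scenarios the bias in the TST contrast runs from 0 to about 21 minutes upward and about 12 minutes downward. The documents do not support reading this as a fault in the main planned comparison, or as a bias that must occur. It is a reversed formula in a conditional missing-data analysis, to be corrected before anyone programs it.

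**What to change.** In the Section 8.2 sentence, change the probability of being missing to the probability of being observed, so that each observed subject is weighted by 1/(1 − P(missing)), with P(missing) taken from the logistic model already planned. In the scenarios above this recovers the 35-minute difference exactly.

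Optional additions are to name the predictors in the logistic model (for example randomized group, age and acuity), to allow group-by-covariate terms, and to use stabilized weights. The error itself does not require them.

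The cost is one amended sentence. Sample size, data collection and the other planned analyses are unaffected.

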8.3 Primary Study Endpoints

8.3.1 Statistical Analysis (Primary Objective)

The primary treatment endpoint for Aim 1 will be generated from PSG. Group comparisons will be made for total sleep time, sleep efficiency, REM, WASO and spectral analysis of C3/C4 delta waves, using a generalized linear random effects model. Secondary analyses will involve adding appropriate covariates to the

model. Age and gender will be retained. Potential covariates include prior experience with HT, medication usage, frequency of random disturbances (such as parents or other caregivers entering the room, cell phones) and number of prior surgical procedures. The same approach will be used to examine hormones, anesthesia emergence, anxiety, and pain scales (Aim 2), the advantage is that the appropriate link function may be applied and we can account for the repeated nature of the design.

Power Analysis

Variable Median (25 th , 75 th percentile)	Healing Touch night N=15	Non-Healing Touch night N=15	p-value
TST minutes	400 (302, 442)	366 (287, 396)	.09
Sleep efficiency %	80 (61, 90)	78 (56, 82)	.07
WASO minutes	72 (47, 160)	85 (82, 181)	.60
REM minutes	86 (62, 93)	63 (40, 97)	.30

The measures targeted are TST, sleep efficiency, REM sleep and WASO. This Table shows data from a pilot cross-over study (median and 25th and 75th percentile) for the sleep variables of interest for 15 study subjects. In order to see the HT group with longer TST than the other groups, we will need a sample size of 50 per group for 80% power to detect a difference of 35 minutes, standard deviation of 70, assuming a 2-sided test and type I error rate of 0.016 to account for multiple testing. Similarly for sleep efficiency, we hypothesize a difference of 2% whereas in a previous study we observed a difference of 10%.³¹ Using the sample size of 50 per group we would be able to detect a difference of 7% with a standard deviation of 15, 2-sided test and type I error rate of 0.016, to account for comparing HT to the 3 control groups. Because the percentages depend upon another time dependent variable, the power is based on REM minutes. Using REM minutes, 50 subjects per group would enable us to detect a 15 minutes difference in REM sleep, assuming a standard deviation of 30, power of 80% and a 2-sided test. For WASO, with an assumed standard deviation of 50, a type 1 error rate of 0.016, a power of 80% and a 2-sided test, a difference of 25 minutes will require 50 subjects in each group, producing a total sample size of 200 subjects.

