The sleep technician will document that an experimental procedure was performed and note any unexpected occurrences (interruptions, HT side effects) at the end of the 1 hour intervention/control period using the demos/safety CRF.

- 4.1.2 Study duration is from approximately 9 pm (when the electrodes are attached for the sleep test) the evening prior to surgery until 8 hours after surgery the following day (unless patient is discharged earlier than 8 hours postop).
- 4.1.3 A description of the sequence and duration of the study procedures are summarized in the below diagram:

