Laboratory parameters (C-reactive protein, glucose, cortisol and D25) will be obtained (from approximately 5 mL of blood) in the operating room. Since there is a strong argument that HT reduces stress and anxiety, the results of this study could provide data demonstrating improved hormonal balance following HT intervention. There also exist reports linking sleep with metabolism of glucose and vitamin D.

An anxiety test (Yale Preoperative Anxiety Scale) will be obtained preoperatively (in patient unit prior to preoperative meds and repeated in the preoperative surgery area).¹⁰⁰ Anesthesia emergence score, sedation score and nausea and vomiting will be assessed in the PACU.¹⁰¹⁻¹⁰³ Incidence of nausea and vomiting in the post recovery patient room (on the floor) will also be recorded.

A patient satisfaction survey will be administered post recovery that includes questions specific to the HT procedure, sleep and also includes four questions identical to that contained in Press Ganey Pediatric Inpatient survey (questions B5, D4, K3 and I9; <http://www.pressganey.com/>) to assess contentment with overall inpatient care.

Implicit in the definition of economic consequences of healing touch, we will also collect select utilization and cost outcome measures including total charges from admission to study discharge as well as charges specific to the Post Anesthesia Recovery Room. Labor cost of HT, length of stay in recovery room (number of minutes), length of hospital stay (number of hours) and medications administered for sleep, anxiety, pain, itch, nausea, vomiting and anesthetics during the defined study period all have high cost implications and thus will be examined as well.

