8.3.2 Statistical Analysis (Aim 2)

Analysis will follow the general approach and then the same specific approach as described for Aim 1, looking at differences in outcomes among groups utilizing generalized linear models. Using this methodology we will be able to examine the differences over time baseline to post recovery, examining the change between time points adjusting for baseline and the interaction between time and group. The secondary approach would examine the difference among groups adding covariates,

accounting for age, gender and other potential covariates such as number of prior surgeries, length of time in surgery and type of surgery (burn related or other).

Using our validation information for the OPAS pain assessment scale¹⁰⁷ with 48 subjects per group, we have a power of $\geq 80\%$ to detect a reduction in pain scale of 0.4 given the standard deviation of 0.52, using a type I error rate of 0.016 (to account for the multiple testing) and 2-sided test. Given the 0.3 difference in pain reduction between preverbal and nonverbal in the validation study, the expected difference appears reasonable. Similarly using prior work performed at our hospital¹⁰³ which examined the rate of postoperative nausea and vomiting after reconstructive burn surgery, with 46 subjects per group we would have 80% power to detect a difference of 69% in the control versus 40% in the HT group with a 2-sided test and type I error rate of 0.05. However after accounting for the multiple testing, using type I error rate of 0.016, the power is reduced to 70% with the 50 subjects per group estimated for the proposed study. Turner et al²⁰ reported on pain after dressing change in older adolescents and adults. In their randomized trial of therapeutic touch; a 23% decrease in anxiety was detected in the intervention group. If we assume that we will see this level of decreased anxiety in the HT group compared to the control and also assume an effect size of 0.7 and a type I error of 0.16, the 50 subjects per group (estimated for Aim 1) would yield 85% power for our analysis of anxiety.

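### The secondary covariate-adjusted analyses may adjust for variables that arise after randomization, and may therefore be biased for the effect of assignment to healing touch

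*Combined protocol and SAP*

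**What the plan says.** Section 4.1.1 randomizes subjects once they have been screened and have agreed verbally, before any study procedure. The session starts at about 2200 that night and surgery follows the next day.

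Section 8.3.1 first sets out the group comparisons on the sleep measures, then secondary analyses with covariates added. Age and gender stay in. For the rest: "Potential covariates include prior experience with HT, medication usage, frequency of random disturbances". The disturbances are parents or caregivers coming in, and phones. The same approach is extended to the Aim 2 outcomes, and section 8.3.3 extends it to Aim 3. Section 8.3.2 names further candidates for Aim 2: "number of prior surgeries, length of time in surgery and type of surgery (burn related or other".

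Section 8.1 treats the duration of the procedure as a baseline characteristic, comparing "differences in baseline variables between HT and control groups (ex. age, gender and race, also length of time and type of surgical procedure".

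Section 8.2 gives the selection rule. A variable enters if it is judged clinically significant, or if it is associated with the outcome and the independent variable of interest at p < 0.15. It stays if p < 0.05, or on the "effect of removal of the variable on the beta coefficient" when that exceeds 10%.

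Medication appears elsewhere as an outcome. Section 2.2 counts medication measures among the postoperative results that HT may improve. Section 4.2 lists as a cost and utilization measure "medications administered for sleep, anxiety, pain, itch, nausea, vomiting and anesthetics during the defined study period".

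No text limits covariates to values known before randomization, and none calls the adjusted result a direct effect or a mediation analysis.

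**The concern.** Randomization makes the arms comparable on everything fixed beforehand. Adjusting for such variables is safe and often gains precision. A variable that arises afterwards is different. If HT changes it, conditioning on it removes or distorts part of the effect of assignment. If it also shares an unmeasured cause with the outcome, conditioning can create an apparent effect where there is none.

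The selection rule adds to this. In a randomized trial a true baseline variable passes a test of association with group only by chance, whereas a variable that HT moves passes it systematically. A change of more than 10% in the group coefficient is likewise what a mediator produces, though chance imbalance produces it too.

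At stake is what the adjusted results mean in all three aims. A reader would take them as refined estimates of the HT effect, and could not tell afterwards how far, or in which direction, they had moved.

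**Working it through.** **1. Timing and role of each candidate**

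| Candidate | When it arises | Does the protocol expect HT to change it? |
|---|---|---|
| Prior HT experience, number of prior surgeries | Before randomization | No; safe |
| Disturbances | Study night; the technician is to "note any unexpected occurrences (interruptions, HT side effects) at the end of the 1 hour intervention/control period" (section 4.1) | Not stated |
| Length of surgery | The next day | Not stated |
| Medication usage | Not dated; the study period runs from about 9 pm to at most 8 hours after surgery | Yes, for study-period medication (sections 2.2 and 4.2) |

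For sleep, the recording stops at about 0600, before surgery, so postoperative drugs cannot lie between HT and sleep. Only drugs given that night could. For Aim 2 the path is direct: analgesics given after surgery affect the pain scores, and the second anxiety rating, in the preoperative surgery area, may follow preoperative medication.

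**2. Algebra**

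The documents give no figure for this bias, so none can be reproduced. Let *a* be the shift in the covariate caused by HT (in SDs) and *b* the minutes of total sleep time per SD of the covariate. In a linear model

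total effect = direct effect + *a* × *b*, so adjusted coefficient = total effect − *a* × *b*.

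If *a* = 0 the two agree.

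**3. Illustration with the plan's selection rule**

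From section 8.3.1: 35 minutes (taken as the true total effect), SD 70, 50 per group. (Those inputs at two-sided 0.016 and 80% power give 85 per group, not the stated 50. That is a separate matter, and nothing here rests on it.) The values of *a* and *b* are assumptions. Each row is 3,000 simulated trials of 50 v 50, with entry at p < 0.15 for both outcome and group, then retention on p < 0.05 or a change above 10%.

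| *a* | *b* | Expected adjusted effect | Simulated | Covariate kept |
|---|---|---|---|---|
| 0 | −30 | 35 − 0 = 35 | 34.7 | 14% |
| −0.2 | −30 | 35 − 6 = 29 | 28.8 | 34% |
| −0.5 | −30 | 35 − 15 = 20 | 19.7 | 85% |
| −0.5 | −40 | 35 − 20 = 15 | 15.1 | 87% |

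The entry screen does almost all the selecting: entry and retention rates are the same to within 0.1 percentage point in every row. In the last three rows the expected change on removal is 6/29 = 21%, 15/20 = 75% and 20/15 = 133%, so the 10% rule removes none of them on average.

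**4. The sign can reverse**

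Suppose instead a night medication that adds 30 to 60 minutes, used by 40% of controls and 10 to 20% of HT subjects (all assumed), with a direct effect of 35 minutes. Total = 35 + *b* × (HT proportion − control proportion):

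- 30 minutes, 40% v 20%: 35 − 6 = 29
- 30 minutes, 40% v 10%: 35 − 9 = 26
- 60 minutes, 40% v 20%: 35 − 12 = 23
- 60 minutes, 40% v 10%: 35 − 18 = 17

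The adjusted model returns 35 each time and so overstates the total effect by 6 to 18 minutes.

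**5. No true effect, shared cause**

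Let HT have no effect on sleep, but shift the covariate by −0.5 SD. Let an unmeasured cause load 0.5 on the covariate and −35 minutes on sleep. The covariate's slope is then 0.5 × (−35) = −17.5, and the adjusted effect is 0 − (−0.5)(−17.5) = −8.75 (simulated −8.7). Rejection at 0.016 is 3.7%, against 1.9% unadjusted.

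**The case against.** The strongest reply is that these models are secondary. Sections 8.1, 8.2, 8.3.1 and 8.3.2 all say so, and the main comparisons come before any covariate. That stands. Because section 8.2 speaks of final models, a reader might infer that the main sleep result is at risk; the documents do not support that.

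Second, the candidates are only potential ones, and medication usage is undated. In section 8.3.1 it is listed with history variables such as prior HT experience, so home medication is a fair reading and would be harmless. That also stands, but it leaves a definition missing.

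Third, being measured after randomization does not make a variable a mediator. A reader might infer that adjusting for disturbances or surgery length must bias the result. No text says HT affects either. If it does not, adjustment does no harm and can help: in the first simulated row, rejection at 0.016 rises from 52% to 61%. What remains is that the arms differ by design in who is in the room, so an effect on disturbances cannot be ruled out in advance.

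Fourth, a change above 10% does not identify a mediator; the rule kept an unaffected covariate in 14% of runs. True, but retention rose to between 85% and 87% when HT moved the covariate by 0.5 SD.

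**Conclusion.** The point holds for the secondary adjusted analyses: as written, they may be biased for the effect of assignment to HT. Medication is the clearest case, above all for pain and anxiety in Aim 2, provided that medication usage means drugs given during the study. For disturbances and surgery length the bias is conditional on an HT effect that the documents do not claim. Calling surgery length a baseline variable is wrong whether or not HT affects it.

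Size and direction cannot be derived from the documents. A reader might take the minutes above as an estimate. They are not: they rest on assumed shifts and slopes, and different assumptions give understatement or overstatement. They show only that the problem need not be trivial against a 35-minute planning difference, and that the selection rule favours the affected variables. This should be fixed before the adjusted results are interpreted; it does not call the unadjusted comparisons into question.

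**What to change.** - In sections 8.3.1 to 8.3.3, restrict adjustment to one prespecified set of values fixed before randomization: the stratification factors as assigned at randomization, age, gender, prior HT experience, number of prior surgeries, planned procedure type and, if wanted, pre-randomization medication. The words on stratification matter because section 4.1.1 defines acuity by the length of stay, which may turn out differently from what was planned.
- In section 8.2, delete the p < 0.15, p < 0.05 and 10%-change rules for choosing covariates.
- In section 8.1, stop listing the length of the procedure among baseline variables.
- Report study-period medication, disturbances and surgery length by arm, or use them in a mediation analysis labelled exploratory.

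The cost is wording only; no new data or subjects are needed. The downside is that variation due to disturbances and surgery length is no longer modelled away, so some precision is lost if HT does not in fact affect them.
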